d. Rationale for Study Design

Based on our current inpatient experience, we believe this protocol can be performed safely at home by subjects and/or their caregivers if given detailed instructions. Subjects who perform intermittent catheterization are being selected because they more likely to have incontinence

than those with an indwelling catheter. If patients are interested, we will trial stimulation in clinic. We will exclude those who we cannot produce toe flexion with posterior tibial nerve stimulation. After 1 week of home stimulation, those that are on bladder medicine will discontinue the medication. There is no other harm from rapid discontinuation of bladder medication, except for incontinence. We expect that incontinence will be reduced from this first week of TTNS. The I-QOL questionnaire is administered at baseline, and at the end of 2 and 4 weeks to determine when best effects of TTNS are achieved.

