2.3. Secondary Objectives

Secondary Objective 1: I-QOL scores will improve and incontinence episodes will reduce after TTNS compared to baseline.

Secondary Objective 2: The frequency of catheterization and the volumes voided will improve with TTNS compared to baseline based on bladder diary.

Secondary Objective 3: Anticholinergic side effects will be reduced based on survey after TTNS protocol.

2.4. Potential Risks and Benefits:

a. End Points - Efficacy

Specific Aim 1: No efficacy requirement for the safety and feasibility studied in specific aim 1.

Specific Aim 2: We expect improved I-QOL scores compared to baseline. As a pilot trial, we have not powered the study for this measure. Results from this study will provide effect size to power a larger study.

b. End Points - Safety

Urinary Tract Infection (UTI) risk:

We expect the rates of morbidity to be the same between those who participate and those who do not. However, because UTI is directly related to the bladder, we will focus on the occurrence of UTI. Based on literature, the overall rate of UTI in SCI is about 2.5 episodes per patient per year. As a result, we expect to see 0.2 episodes per patient during the 4-week study period. Based on that, we construct the stopping rules to stop at 20% UTI rate using lower 90% exact Blyth-Still-Casella confidence bounds. If the number of patients with UTI exceed 3 in the first 5 patients, 4 in the first 10 patients, or 5 in the 14 patients, then patient accrual will be paused pending a review by a medical advisory board comprised of SCI experts.

Bladder medication discontinuation risk:

- Worsened incontinence

Electric Stimulation Risks:

Electric stimulation is commonly performed on the extremities of those with spinal cord injury at the study institution. There are few adverse reactions to electric stimulation. The common ones include:

- Pain with electric stimulation: in these cases, the intensity is reduced until it is comfortable.
- Skin irritation: it is common for redness to occur on the skin at the site of the surface electrode. This typically dissipates within an hour of removing the electrode. In some cases, the redness remains the next day. In these cases, they are likely sensitive to the adhesive used and a hypoallergenic skin electrode will be provided.

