3.5. Withdrawal Criteria

Possible reasons for discontinuation of study intervention:

- Intolerable incontinence after discontinuation of bladder medications
- Intolerant to electric stimulation
- Non-compliance

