11.2. Statistical and Analytical Plans

This pilot study will serve as an earlier-phase developmental function that will enhance the probability of success in a larger subsequent randomization intervention trial.

In Aim 1, for safety, we hypothesize that there will be no unusual adverse events. However, because UTI is directly related to the bladder, we will focus on the occurrence of UTI. Based on literature, the overall rate of UTI in SCI is about 2.5 episodes per patient per year.¹⁸ As a result, we expect to see .2 episodes per patient during the 4-week study period. Based on that, we construct the stopping rules to stop at 20% UTI rate using lower 90% exact Blyth-Still-Casella confidence bounds. If the number of patients with UTI exceed 3 in the first 5 patients, 4 in the first 10 patients, or 5 in the 14 patients, then patient accrual will be paused pending a review by a medical advisory board comprised of SCI experts.

For feasibility and compliance, we will calculate descriptive statistics to determine the dropout rate and percent of adherence to the prescribed regimen as well as program satisfaction. If the dropout rate is less than 25%, and if subjects complete greater than 70% of daily TTNS use in the 4-week period, we will consider the study has high feasibility/adherence. If more than 80% of subjects report that they were satisfied with the program, then we will consider the study has high satisfaction.

In Aim 2, descriptive statistics will be provided for incontinence episodes, catheterization frequency, volumes voided, and anticholinergic-related side effects after the TTNS. The results along the time will be compared to baseline by paired t test, signed t test, or repeated measure methods when appropriate. Since this is an exploratory study and the efficacy of TTNS in this study will be further studied in future larger studies, Bonferroni correction will not be necessary. TTNS satisfaction will be based on the scores of a TTNS survey and descriptive analysis will be provided as well. We will also check the association between these changes from baseline, as well as bladder medication associations.

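### Worsened incontinence is listed under the safety end points as the expected harm of stopping the bladder drug, but the Aim 1 safety analysis does not count it

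*Combined protocol and SAP*

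**What the plan says.** Section 1.2 d sets the drug stop as a protocol step: "After 1 week of home stimulation, those that are on bladder medicine will discontinue the medication". It adds: "There is no other harm from rapid discontinuation of bladder medication, except for incontinence". Section 2.4 b, under its safety end points subheading, gives one item as the risk of that step: "Worsened incontinence". Section 3.5 lists "Intolerable incontinence after discontinuation of bladder medications" among the possible reasons to discontinue. Safety is part of Primary Objective 1 (section 2.2).

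The Aim 1 safety analysis in section 11.2 has two parts. The first is general: "for safety, we hypothesize that there will be no unusual adverse events". The second is specific: "because UTI is directly related to the bladder, we will focus on the occurrence of UTI", with a rule for pausing accrual that counts patients with UTI only. Incontinence enters under Aim 2, where "descriptive statistics will be provided for incontinence episodes, catheterization frequency, volumes voided", followed by comparison with baseline using a paired t test, a signed t test or repeated-measures methods.

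Subjects who drop out are replaced (section 3.6). Withdrawal, for whatever reason, requires no final evaluation (section 6.4).

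**The concern.** Worse incontinence is the one harm the protocol foresees from its own drug stop. Because it is foreseen, it is not clearly an unusual event, so the first part of the Aim 1 analysis need not pick it up; the second part is about UTI. The study could meet its safety hypothesis without saying how many subjects became worse after the stop.

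The Aim 2 comparison does not fill the gap, for three reasons. A mean change does not show how many subjects moved the wrong way. Only subjects on a bladder drug are exposed to the stop, and the plan does not separate them from the others in the comparison. The subjects most harmed are also the ones most likely to leave, and they can then be missing from the paired data.

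**Working it through.** **1. The plan's own safety figure.** Section 11.2 takes the literature to show that "the overall rate of UTI in SCI is about 2.5 episodes per patient per year". Over four weeks, 2.5 × 4/52 = 0.192, which rounds to the stated 0.2, so the figure reproduces. It underlies the only quantified safety analysis. No rate, definition or count is given for worsened incontinence.

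**2. Incontinence traced through the plan.**
- Expected harm: section 1.2 d and section 2.4 b.
- Data: the diary logs each episode (section 5), and weekly calls collect the entries (sections 6 and 6.4).
- Monitoring: section 9.3 speaks of morbidity rates, compared with controls that a single-arm study does not have, then narrows to UTI.
- Analysis: Aim 2 of section 11.2 only.

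No section defines worsening or plans a count of subjects who worsen.

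**3. What the withdrawal path allows.** Section 5 expects 20 enrolled and 4 lost. Section 11.2 calls feasibility high if dropout is below 25%, and does not plan dropout by reason. Since 4/20 = 20% passes and 5/20 = 25% does not, up to four subjects could leave for intolerable incontinence with the dropout criterion still met. This assumes that discontinuation under section 3.5 is handled as dropout under section 3.6. The exact 95% CI for 4/20 is 5.7% to 43.7%.

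**4. What a group mean can conceal (illustration).** The documents give no mean or SD for the change, so the effect sizes are assumed. Analysed n = 20 − 4 = 16. If changes are normal with a mean improvement of d SDs, the share showing an increase is Φ(−d), and the paired test has t = d√n on n − 1 df.
- d = 0.7, n = 16: t = 0.7 × 4 = 2.80, p = 0.013; Φ(−0.7) = 24%.
- d = 0.55, n = 16: t = 2.20, p = 0.044; Φ(−0.55) = 29%.
- d = 0.7, n = 14 (the number section 11.1 calls sufficient): t = 2.62, p = 0.021.

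Normality is not essential. If 10 of 14 improve by 2 episodes a day and 4 worsen by 1, the mean is (−20 + 4)/14 = −1.14, the SD is 1.41, t = −3.04 and p = 0.009, with 4/14 = 29% worse.

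**5. Why step 4 is not a harm rate.** It treats every analysed subject as exposed to the drug stop and measures change from baseline rather than from week 1. It also counts any increase, including day-to-day variation. With the same observed 25%, the exact 95% CI depends on how many stop a drug: 4/16 gives 7% to 52%, 2/8 gives 3% to 65%, and 1/4 gives 1% to 81%.

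**6. How a count should be defined.** Take a subject whose true rate λ does not change, with X ~ Poisson(7λ) episodes in week 1 and Y ~ Poisson(21λ) in the 21 days after the stop. P(Y/21 > X/7) is 0.49 for each of λ = 0.3, 1 and 2 a day (rates assumed). Counting any increase would therefore label about half of unchanged subjects as worse. With a minimum rise of 1 episode a day, P(Y/21 − X/7 ≥ 1) is below 0.001, 0.008 and 0.052 at the same three rates. The value of 1 only shows that a margin controls the error; it is not a proposed margin.

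**The case against.** The strongest reply is that the plan would see worse incontinence by other routes.
- Section 9.1 defines an adverse event broadly enough to include it, section 9.2 provides for collection and grading, and section 9.3 for quarterly review.
- The diary and weekly calls record every episode.
- If the signed t test in section 11.2 means a sign test, it rests on how many subjects move in each direction.
- Section 11.2 also plans a check of associations with bladder medication, and a dropout rate that would include those who leave for incontinence.

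A second reply is that section 2.4 as a whole concerns risks and benefits, so the item may be risk disclosure rather than an outcome to analyse. A third is that a small exploratory pilot need not analyse everything.

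Much of this stands. A reader might infer that the plan has no means of noticing worse incontinence; the documents do not support that, because the data are collected and adverse events are defined widely. What the replies do not supply is a reported number of subjects who worsened. Incontinence is not named in the monitoring text, the medication check is undefined, the sign-test reading is a guess and would pool exposed with unexposed subjects, and dropout is not split by reason. The wording of section 2.4 is ambiguous, but the subheading is about safety end points, and on either reading this is the foreseen harm of a study step in a trial whose primary aim includes safety. Pilot status is a reason not to require a test or power, which a descriptive count does not need.

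**Conclusion.** The point holds as a gap in the analysis plan, not in data collection. Followed as written, section 11.2 allows a favourable safety conclusion that does not account for the expected harm of the drug stop, and subjects who leave because of that harm can drop out of the only incontinence comparison. The change is worth making because it affects what the primary safety conclusion rests on.

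The size of any actual harm cannot be derived from the documents. A reader might take the 24% or 29% above as the share likely to be harmed by stopping the drug. That reading is not supported: the figures rest on assumed normal changes and assumed effect sizes, and the number of subjects on a bladder drug is not stated. Nor do the documents show that the drug stop is unsafe; the point is only that the planned analysis would not say.

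**What to change.** In section 11.2, Aim 1, add a safety summary beside the UTI result, covering all enrolled subjects who stop a bladder drug, including those later replaced:
- (a) the number and percent, with exact 95% CI, who discontinue for intolerable incontinence;
- (b) each subject's change in incontinence episodes per diary day after the stop compared with week 1, and the number and percent (exact 95% CI) whose increase exceeds a minimum fixed before the data are seen. Subjects in (a) count as worsened in (b).

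State the denominator, and do not define worsening as any increase. The investigators should choose the minimum and record their reason for it.

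The cost is one table from diary data and withdrawal reasons, with no added visits. It has two limits. The summary is descriptive with wide intervals: even 0 of 14 has an exact 95% CI of 0 to 23.2%, and fewer exposed subjects would widen it. And week 1 already includes TTNS, so the comparison addresses the drug stop while on TTNS and says nothing about TTNS itself.

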3. STUDY POPULATION

3.1. List the number of subjects to be enrolled.

Consecutive SCI clinic encounters meeting the inclusion/exclusion criteria will be asked to enroll. Children and pregnant women will be excluded.

3.2. Criteria for Recruitment

- Initial screening will be performed in the clinic with the subject and PI
- In those interested, they will be given an IRB-approved consent form to review and to sign.
- Those with tetraplegia will unlikely have the ability to sign and we will have a 3rd party attest to the consent.
- Patients will ideally decide to participate in clinic, but can always decide at a later date and return to clinic to trial the TTNS as part of the I/E criteria.

3.3. Inclusion Criteria (table 1)

Table 1. Inclusion/ Exclusion Criteria

| Inclusion | Exclusion |
|------------------|---|
| 18-65 years old | Multiple medications for the bladder Cancer in the tibial nerve path and/or bladder. |

| | | |
|---|---|--|
| Neurologically stable SCI for ≥ 6 months | Other diagnoses to explain incontinence (ex: UTI, bladder stones, multiple sclerosis, etc.) | Inability to elicit toe/plantar flexion with electric stimulation during clinic visit. |
| Intermittent catheterization to empty bladder | 2+ pitting edema that does not resolve | Inability to understand directions |
| Stable bladder medications for ≥ 3 months | Known peripheral neuropathy or injury to the path of the tibial nerve | Non-English speaking |
| | Demand-type cardiac pacemaker or implanted defibrillator | |

3.4. Exclusion Criteria (table 1)

Patients on multiple bladder medications will be excluded for the rationale that they have a severely dysfunctional bladder that requires multiple bladder medications, likely having developed over many years. It is unlikely that TTNS alone can benefit this population and it would skew the results for efficacy.

Patients with known etiologies of incontinence other than SCI will be excluded.

Those patients with severe lower leg edema will be excluded because in our current trial, we have found that the electric current does not elicit toe flexion in those with extensive leg edema.

For electric stimulation, we exclude those that have an implanted cardiac device, cancer at the stimulation site, and those that we cannot elicit toe flexion in clinic.

3.5. Withdrawal Criteria

Possible reasons for discontinuation of study intervention:

- Intolerable incontinence after discontinuation of bladder medications
- Intolerant to electric stimulation
- Non-compliance

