1. BACKGROUND AND RATIONALE

There are over 1 million people living with spinal cord injury (SCI) with devastating functional impairments including paralysis and bowel/bladder dysfunction.¹ Nearly every person with SCI develops neurogenic bladder.² The gold-standard treatment of neurogenic bladder involves the use of anticholinergic bladder medications, which suffers from non-compliance and adverse medication effects.³ Improving bowel and bladder function is the number one priority that people living with SCI wish to achieve.⁴ Treatments such as bladder neuromodulation with tibial nerve stimulation (TNS), have been shown to improve bladder function in SCI without adverse effects.^{5,6} Percutaneous TNS (PTNS) is performed using a needle inserted into the skin to direct the electric current, provided by trained healthcare workers in the clinic setting under physician supervision. This requires frequent visits in a population with known accessibility challenges. Transcutaneous TNS (TTNS) accomplishes the same goal, but uses non-invasive surface electrodes. However, this modality has only been performed in the clinic setting. There is currently a gap in our knowledge about the safety and feasibility of TTNS at home for bladder neuromodulation in SCI. The proposed research is innovative, in our opinion, because it represents a substantive departure from the status quo by using TTNS at home to replace anticholinergic medications and provide a dignified treatment that can improve quality of life.

Electric stimulation is routinely being used in neurorehabilitation. The PI has published reviews on the current state of rehabilitation in SCI, describing the use of FES and NMES in SCI for motor/sensory recovery, decreasing spasticity, and improving neuropathic pain.^{9, 10} Patients are routinely prescribed electric stimulation units for home use to help with motor recovery and strengthening. We propose the development of a protocol that uses the same equipment in a novel way to effect bladder function.

We are currently using the proposed TTNS protocol for research purposes (HSC-MS-15-0806) at TIRR for acute SCI during their inpatient rehabilitation admission (Table 1). Based on the preliminary safety data, we believe we can develop this protocol for home use (Table 2).

Table 1. Preliminary data demographics of subjects inpatient TTNS protocol

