2. HYPOTHESIS AND OBJECTIVES

2.1. Hypothesis

Specific Aim 1: **Determine the safety, feasibility, and compliance of a daily home TTNS protocol in chronic SCI provided by self or caregiver for 4 weeks.**

Hypothesis 1.1: TTNS at home is safe and feasible with high compliance.

Hypothesis 1.2: TTNS protocol will demonstrate overall satisfaction as a neurogenic bladder treatment option based on survey questionnaire.

Specific Aim 2. **Determine the efficacy of a 4 week TTNS protocol.**

Hypothesis 2.1: Incontinence quality of life scores and frequency of incontinence will improve with TTNS compared to their baseline.

Hypothesis 2.2: Frequency of catheterization and volumes voided will improve with TTNS compared to baseline measurements.

Hypothesis 2.3: Anticholinergic-related side effects will improve with TTNS after discontinuation of bladder medications

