3.6. Subject Replacement

Subjects who drop out will be replaced by recruitment from the SCI clinic and asking for informed consent from those who meet the I/E criteria.

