6.4. Study Visits and Procedures

- *Screening Visits and Procedures*

Screening will be performed in the SCI clinic by the PI and co-I SCI attendings.

Those that meet the I/E criteria will be approached for the study by the PI and co-I attendings. They have until the study period is complete to decide whether they want to participate. However, they will have to return to clinic to have the TTNS trial performed and the directions for home use.

- *Study Visits and Procedures*

Subjects will have their first study visit after their normal clinic visit. Once consented, we will trial TTNS for a response of toe flexion. If they have a response, they will be included in the study. If no response or not tolerating electric stimulation, they will not be included in the study.

Participants will have direction in clinic on the use of the Stambil+, including written, oral, and smartphone images/video if they have access.

The electric stimulation protocol will use stimulation frequency of 10 Hz and pulse width of 200ms in continuous mode for 30 minutes daily, beginning as soon as possible. For sexually active women of child-bearing age, the home use will begin after the results of a pregnancy test are provided. The goal is daily use of TTNS for 4 weeks.

Subjects will be called weekly to capture the information from the bladder diary log and to monitor progress of protocol. They will also be reminded to change electrodes weekly.

- *Final Study Visit:*

Upon completion of the 4-week protocol, subjects will return with the stimulator and the bladder diary.

- *Post Study Follow up and Procedures*

The data will be statistically analysed in the post-study follow up. Subject participation is not required.

- *Discontinuation Visit and Procedures*

If withdrawal occurs, no evaluation will be required for the final study visit, regardless of the withdrawal reason. There are no safety risks in withdrawing from this study at any point.

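### Subjects withdrawn for intolerable incontinence off the bladder drug have no required week-4 outcome, so the week-4 Aim 2 change and the effect size taken from it are biased toward benefit

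*Combined protocol and SAP*

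**What the plan says.** The Background (section 1) describes the innovation as "using TTNS at home to replace anticholinergic medications". Section 1.2(d) sets the sequence: "After 1 week of home stimulation, those that are on bladder medicine will discontinue the medication". On measurement it says "The I-QOL questionnaire is administered at baseline, and at the end of 2 and 4 weeks". The schedule in section 4 puts the follow-up side-effect questionnaire at week 4 only, and one hypothesis in 2.1 depends on it: "Anticholinergic-related side effects will improve with TTNS after discontinuation of bladder medications".

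Section 3.5 gives three possible reasons for discontinuing the study intervention. The first is "Intolerable incontinence after discontinuation of bladder medications"; the others are intolerance of stimulation and non-compliance. Section 3.6 states "Subjects who drop out will be replaced by recruitment from the SCI clinic", with no exception by reason. Section 6.4 adds "If withdrawal occurs, no evaluation will be required for the final study visit, regardless of the withdrawal reason".

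For Aim 2, section 11.2 says "The results along the time will be compared to baseline by paired t test, signed t test, or repeated measure methods when appropriate". It names no analysis set, no rule for missing outcomes and no sensitivity analysis. Withdrawals enter 11.2 only through the Aim 1 dropout rate, judged against 25% without regard to reason. Section 2.4 says that Aim 2 is unpowered and that its results will supply the effect size for a larger study.

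**The concern.** Incontinence is an Aim 2 outcome. A subject who stops the drug, finds the incontinence intolerable and withdraws has one of the worst Aim 2 results the study can produce. Under 3.6 and 6.4 that result need not be measured at week 4, and another subject is recruited. Missing week-4 data are then related to the outcome itself, and the subjects left in a week-4 paired test are selected for having done better.

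Two things are at stake. The week-4 change from baseline would look better than it is, and the effect size carried into the larger study would be too large, so that study would be too small. In addition, the most direct evidence on whether TTNS can stand in for the drug would be recorded only as part of an undivided dropout rate.

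**Working it through.** **Inputs from the plan.** Enrolment is 20, with 4 anticipated dropouts or losses (section 5). Section 11.1 regards 14 as sufficient and treats the number as a convenience sample. I-QOL is taken at baseline, week 2 and week 4.

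**The plan's own figure.** The expected loss is 4/20 = 20%, leaving 20 − 4 = 16, which exceeds 14. Inflating 14 for 20%, 25% or 30% loss gives 14/0.80 → 18, 14/0.75 → 19 and 14/0.70 = 20. Enrolling 20 is consistent with the plan, and the sample size is not in dispute.

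**Who can enter the week-4 test.** A paired change is the week-4 value minus the baseline value. A subject withdrawn after the drug is stopped has a baseline value but no required week-4 value, so there is no difference to analyse. If withdrawal comes before the end of week 2, there is no required I-QOL off the drug at all.

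**Assumptions not in the plan.** The test is two-sided at 5%, so upper-tail rejection is 2.5% if nothing is wrong. Changes are normal with SD 1 and true mean 0. The subjects lost are those lowest on a tolerance scale that has correlation ρ with the change. The plan gives neither ρ nor the share of losses due to incontinence, so a range is shown.

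**Closed-form check.** With the worst 20% removed, the mean of the rest in a large sample is φ(z₀.₂₀)/(1 − 0.20) = 0.350 SD. For exactly 4 of 20 the simulated value is 0.333 SD, and at correlation ρ the shift is ρ × 0.333: for example 0.5 × 0.333 = 0.167.

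**Simulation (100,000 trials per row, true change zero).**

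| Loss | ρ | Analysed | Shift in mean (SD) | Upper-tail rejection |
|---|---|---|---|---|
| 4 of 20 | 0.3 | 16 | +0.10 | 6% |
| 4 of 20 | 0.5 | 16 | +0.17 | 10% |
| 4 of 20 | 0.8 | 16 | +0.27 | 23% |
| 4 of 20 | 1 (worst first) | 16 | +0.33 | 38% |
| 1 of 20, the worst responder | 1 | 19 | +0.10 | 7.5% |
| 4 of 20, only one of them the worst responder | – | 16 | +0.10 | 7% |
| 4 of 24, replaced so that 20 complete | 0.5 | 20 | +0.14 | 10% |
| 4 of 24, replaced so that 20 complete | 1 | 20 | +0.29 | 35% |

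Replacement lowers the shift slightly, because 4/24 is a smaller fraction than 4/20, but does not remove it.

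**If stopping the drug itself worsens incontinence.** Baseline is then on drug and follow-up off drug, so a useless treatment would give a negative true change. With 4 of 20 lost worst first, a true change of −0.2, −0.3 or −0.5 SD gives upper-tail rejection of about 12%, 6% or 1%. At ρ = 0.5 the figures are about 2%, 0.8% and 0.1%. The shift does not depend on the true mean: at −0.3 SD, worst first, completers average −0.30 + 0.33 = +0.03 SD, so a real worsening is reported as no change.

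**Visibility in Aim 1.** Four withdrawals off drug among 20 give 20%, below the 25% limit. The dropout part of the feasibility criterion would be met, with no sign that all four were failures off the drug.

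**The case against.** The strongest reply has four parts.

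- **Scope.** A reader might infer that only subjects who coped off the drug are tested. The plan does not support that. Section 1.2(d) stops the drug in those who are taking it, which leaves room for subjects on none, and they would be tested too. Section 3.5 lists possible reasons, so withdrawal is permitted and not automatic. No section says that withdrawn subjects' data are discarded. Their absence from the week-4 test is inferred from the lack of a required value.
- **Data that may exist.** Diary data are collected by weekly call, and I-QOL is also taken at week 2. A subject who fails may therefore contribute some off-drug diary entries and perhaps one I-QOL, and 11.2 allows repeated-measures methods that could use them. This stands as a limit: the loss is surest for the week-4 I-QOL and side-effect questionnaire. But 11.2 does not commit to using these values, and a repeated-measures model does not by itself correct for dropout driven by the outcome.
- **Error rate.** A reader might take 38% as the false-positive rate for a useless treatment. It is not. It needs every expected loss to be the worst responder and a true change of exactly zero. Section 2.4 itself names worse incontinence as the risk of stopping the drug, and sections 3.5, 5 and 11.1 give other causes of loss. This objection stands in full for the error rate. It does not touch the shift in the mean.
- **Status of Aim 2.** It is exploratory and unpowered, 11.2 will look at associations with bladder medication, and a drug-free proportion is not among the stated objectives. All true. But the effect size is meant for use in planning, and section 3.4 already excludes one group because it would distort the efficacy result, so the plan itself treats selection as important.

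**Conclusion.** The concern holds in a bounded form. Read together, sections 3.5, 3.6, 6.4 and 11.2 leave subjects who fail off the drug without a required week-4 outcome, and no analysis rule brings them back. The week-4 Aim 2 change is therefore biased toward benefit.

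On the plan's own expected loss, the shift is +0.10 to +0.33 SD for ρ from 0.3 to 1, and about +0.10 SD if just the single worst responder is lost. The rejection rates in the table hold only for a true change of zero; a negative true change lowers them. The lasting harm is to the estimate and to the planning of the next study, more than to a significance claim. The size rests on assumed values for ρ and for the share of losses due to incontinence, which the plan does not give.

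The documents do not show that withdrawn subjects will be deliberately excluded, that everyone tested stopped a drug, or that a useless treatment would be declared effective 38% of the time.

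**What to change.** Change sections 11.2 and 6.4 as follows.

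1. Define the Aim 2 analysis set as everyone who started home TTNS. State that replacements are added to withdrawn subjects and do not take their place in any denominator.
2. Ask for I-QOL and diary data by phone at withdrawal, and again at week 4 where the subject agrees. Use every post-baseline value collected, including the week-2 I-QOL and the weekly diary.
3. Record the reason for withdrawal; no section says this will be done. Among all who stopped the drug, report the proportion still on TTNS and off bladder medication at week 4. Count withdrawal for intolerable incontinence, or resumption of the drug, as failure.
4. Add a sensitivity analysis using a signed-rank test, with worst rank for withdrawals due to intolerable incontinence. Because ranks give no mean or SD for planning, also give the completer mean and SD, labelled as completer-only and likely optimistic.

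The cost is one form field, a short phone questionnaire and some added text in the analysis plan. The drug-free proportion is a new descriptive result and should be presented as one. The headline change may be less favourable. No change to the clinical withdrawal rule is proposed.
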